Hospitalisation	NHS service use	In relation to infections; number of hospital stays for all-cause hospitalisation (as recorded in care home records and discharge summaries)	In a 12 month* period (data recorded at regular intervals by RN from care home records)
Mortality	Mortality rates	Total number of deaths of trial participants (collected from care home records)	In a 12* month period (data recorded at regular intervals by RN from care home records)
Antimicrobial resistance	Gastrointestinal colonisation with antimicrobial resistant (AMR) bacteria	Culture and antibiotic sensitivity of Gram-negative Enterobacteriaceae and vancomycin resistant enterococci (VRE) from stool sample	Samples taken at baseline, 3* and 12* months
Oral microbiology	Levels of oral Candida	Semi quantitative analysis of oral rinse or saliva samples	Samples taken at baseline, 3* and up to 12* months
Influenza vaccine response (for those who have received influenza vaccine only)	Influenza vaccine efficacy	Blood sample - Haemagglutinin inhibition assay and antibody titers	Sample taken on the day of (or up to 10 days prior to), and 4 weeks (28 days) post influenza vaccination (trial participants need to have been on Study Product for at least 2 months prior to influenza vaccination to take part in this sub-study)
Immunology (ex-vivo responses to	Participant's cytokine and chemokine response in whole	Response measured by laboratory analysis in whole blood (stimulated ex-vivo by TLR2 and TLR4 agonists)	Baseline and up to 12* months

pathogenic challenge) (n≈100)	blood samples stimulated ex-vivo by TLR2 and TLR4 agonists  Participant's plasma cytokines and chemokines  Participant's monocyte and neutrophil phagocytosis of E.coli	Measurement of plasma cytokines and chemokines in plasma and whole blood  Measurement of monocyte and neutrophil phagocytosis of E.coli	Baseline and up to 12* months  Baseline and up to 12 months*
Gut microbiology	Quantify the amount of probiotic in stool samples	Investigative work to analyse level of Lactobacillus rhamnosus , LGG and Bifidobacterium animalis subsp. lactis , BB-12 from stool sample	Samples taken at baseline, 3* and up to 12* months
Haematology and Biochemistry	Haematology; biochemistry	Full blood count (FBC) including immune phenotyping; vitamin D	FBC and Vitamin D at Baseline (all participants); FBC on n≈100 (immunology participants only) and up to 12 months

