### 15.2 Data collection/assessment

Eligible participants or their consultee will have an appointment arranged at which informed consent or a consultee declaration (see section 10.3) will be obtained. A second baseline appointment will be made, at which baseline samples will be taken, and baseline data recorded.

The follow-up schedule will depend on the length of time that a participant has been in the study.

Where possible, participants will have a baseline assessment, and three- and 12-month follow-ups (participants randomised pre-December 2017).

Due to time limitations, some participants may have a truncated follow-up and will receive either a baseline assessment and 3 month follow-up (those randomised in May 2018), or a baseline

assessment, 3 month follow-up and a second follow-up between 6-10 months post-randomisation (those randomised between December 2017 and April 2018).

The target window for the 3-month follow-up is -2/+4 weeks.

The target window for the 12-month follow-up is 11 months +/- 1 month.

Infection, antibiotic use, adverse events and study product use will also be recorded by the RN from care home notes at regular intervals using the weekly record forms for 12 months post randomisation or until 31/10/18, whichever is sooner.

A sub-set of patients who have been taking the study product for a minimum of two months and who have had an influenza vaccination after the two month period will have an appointment arranged to attend a third appointment about four weeks (28 days) after the influenza vaccine.

Influenza vaccinations will be administered via routine care. The date of administration will be recorded.

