## 18.2 Description of outcomes and method of statistical analysis

Outcome	Main analysis	Sensitivity analyses*
Primary		
Cumulative antibiotic administration days (CAAD)	Poisson regression.	Negative binomial regression (if Poisson over-dispersed).
Secondary		
CAAD by infection (UTI, RTI, skin, GI, unexplained fever)	Poisson regression, with trial arm interacted with infection.	Negative binomial regression (if Poisson over-dispersed).
Incidence of infection	Poisson regression.	Negative binomial regression (if Poisson over-dispersed).
Site of infection	Poisson regression, with trial arm interacted with infection.	Negative binomial regression (if Poisson over-dispersed).
Mean duration of infection	A two-level Cox PH (frailty) model with infections nested within participants.	
Cumulative number of infection days	Poisson regression.	Negative binomial regression (if Poisson over-dispersed).
Antibiotic-associated diarrhoea Incidence and duration	Poisson regression.	Negative binomial regression (if Poisson over-dispersed).
All- cause diarrhoea (incidence and cumulative days)	Poisson regression.	Negative binomial regression (if Poisson over-dispersed)
Mean duration of diarrhoea episodes	A two-level Cox PH (frailty) model with infections nested within participants.	
Secondary – Health Utility		
Health utility (EQ5D)	Two linear regressions (EQ5D at 3/12 months separately) controlling for baseline EQ5D.	Transformations for normality.
Well-being (ICECAP-O)	Two linear regressions (ICECAP-O at 3/12 months separately) controlling for baseline ICECAP-O.	Transformations for normality.
Hospital stays	Logistic regression.	Poisson/negative binomial regression of counts (mean rate of hospital stays).
Death	Logistic regression.	Cox PH model for time from randomisation to death.
Secondary - Antimicrobial		

Resistance		
Presence of Gram-negative isolates in stools	Two logistic regression (stool sample finding at 3/12 months separately) controlling for baseline stool sample finding.	
Vancomycin resistant enterococci in stools	Two logistic regressions (stool sample finding at 3/12 months separately) controlling for baseline stool sample finding.	
Secondary - Mechanistic		
Immune parameters -Immune cell phenotypes -TLR ligand stimulated cytokines/chemokines -Plasma cytokines/chemokines -Monocyte and neutrophil phagocytosis -Flu vaccine response	Linear regression.	Transformation for normality.

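### The number of hospital stays is analysed mainly as any versus none over follow-up of about 5 to 12 months, with the rate model left as sensitivity; death has a lesser form of the same problem

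*Protocol*

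**What the plan says.** In the table of section 18.2, the main analysis for both hospital stays and death is "Logistic regression". The sensitivity column gives "Poisson/negative binomial regression of counts (mean rate of hospital stays") for hospital stays and "Cox PH model for time from randomisation to death" for death. The same table names ordinal regression separately for another outcome, so logistic here means a yes/no response.

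Section 5.1 states the hospitalisation outcome as "number of hospital stays for all-cause hospitalisation". For mortality the objective is "Mortality rates" and the outcome measure is "Total number of deaths of trial participants". Both are assessed over 12 months, with an asterisk leading to a note on shortened follow-up.

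Section 15.2 explains: "Due to time limitations, some participants may have a truncated follow-up". Weekly-record collection runs to 12 months or 31/10/18, whichever comes first. Residents randomised from December 2017 to April 2018, and in May 2018, have shortened schedules.

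**The concern.** For hospital stays, the variable in the main analysis is not the outcome that section 5.1 defines. A resident with four admissions counts the same as a resident with one. Section 18.2 treats the other event counts differently: infection incidence, cumulative infection days and diarrhoea incidence all have Poisson regression as the main analysis. No reason is given for the exception.

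A yes/no response also needs a time horizon. The EQ5D, ICECAP-O and stool-sample rows are tied to the 3- and 12-month visits, but the rows for hospital stays and death name no time point and no adjustment for time at risk. Since the calendar cap makes that time unequal, the odds ratio describes a mixture of follow-up lengths particular to this trial's recruitment pattern. Precision on hospital stays and the interpretability of both results are at stake.

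**Working it through.** **Figures in the plan.** The protocol gives no power or event number for hospital stays or death, so there is no figure of its own to reproduce for them. The nearest is at least 82% power for the primary outcome (section 17.2). With a mean of 17.4 × 250/365 = 11.92 days, an exact 10% reduction and 129 or 135 per arm, a two-sided 5% Poisson comparison gives 81.2% and 82.9%. With 15.6 against 17.4 days it gives 83.8% and 85.4%. That figure is sound and does not enter this point.

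**Time at risk (section 15.2, cap 31/10/2018).**

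| Randomised | Days to cap | Months |
|---|---|---|
| 31 May 2018 | 153 | 5.0 |
| 1 May 2018 | 183 | 6.0 |
| 1 December 2017 | 334 | 11.0 |
| 31 October 2017 | 365 | 12.0 |

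**Chance of any stay.** Section 4.2 cites 167 admissions in 240 residents over a year: 167/240 = 0.696 per resident-year. At a constant rate, P(any stay by t) = 1 − exp(−0.696 t).
- 5 months: 1 − exp(−0.290) = 0.252
- 12 months: 1 − exp(−0.696) = 0.501

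The risk roughly doubles between the shortest and longest follow-up.

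**Information kept by any/none.** For a Poisson count with mean λ, the information on log λ is λ from the count and λ² exp(−λ)/(1 − exp(−λ)) from any/none. The ratio is λ exp(−λ)/(1 − exp(−λ)).
- 12 months, λ = 0.696: 0.696 × 0.499/0.501 = 0.69, so 31% is lost.
- 250 days (the mean in section 17.2), λ = 0.696 × 250/365 = 0.477: 0.477 × 0.621/0.379 = 0.78, so 22% is lost.

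For a negative binomial count with mean μ and known dispersion 1, the information is μ/(1 + μ) from the count and μ/(1 + μ)² from any/none. The ratio is 1/(1 + μ) = 1/1.70 = 0.59 at μ = 0.70, so 41% is lost. Over-dispersion makes the loss larger.

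**Power for stays, by simulation.** Assumptions: 155 per arm (310 recruited, Appendix 1 Background), half with 5 to 11 months of follow-up, 0.696 stays per year, rate ratio 0.7, 3000 runs. The rate model uses a robust variance.

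| Dispersion | Logistic | Rate model |
|---|---|---|
| 0 | 48% | 60% |
| 0.5 | 39% | 51% |
| 1.0 | 30% | 43% |

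With no effect, logistic rejected in 4.0% to 5.1% of runs and the rate model in 5.0% to 5.7%, so a small part of the gap at dispersion 0 may reflect test size.

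**Death, same design.** The protocol gives no death rate, so annual control risks of 15% and 25% are assumed. The risk at 5 months is then 6.5% and 11%. With a hazard ratio of 0.6, power is 28% for both the logistic and the person-time model at 15%, and 44% for both at 25%. With no effect and no withdrawal, logistic rejected in 4.7% and 5.5% of runs.

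**The case against.** Several points on the other side stand.

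- A reader might infer that unequal follow-up biases the comparison. It does not by itself: allocation is 1:1 and minimised within care home (section 17.1), so follow-up length is balanced in expectation, and simulated type I error for logistic regression stayed at 4.0% to 5.5%.
- A reader might also infer that every resident who withdraws or moves is scored as event-free. Nothing in the protocol says so. Section 18.1 plans missing-at-random methods for drop-out, with sensitivity analyses and separate treatment of health-related moves. Section 11 lets routine-record collection continue after some withdrawals. If withdrawal were assumed to be 10% against 25% per year and withdrawn residents were counted as alive, a true null would give an odds ratio of about 0.91, against a person-time ratio of about 1.0. Both conditions are assumptions from outside the document.
- A total number of deaths fits a proportion as well as a rate, so for death the mismatch with section 5.1 is weak.
- Both outcomes are secondary and the better-fitting models are already prespecified, so both sets of results would be reported.
- The SAP, not seen here, may add detail on follow-up.

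Two things remain. The ranking of main over sensitivity analysis is fixed in the protocol itself. The missing-data text in section 18.1 deals with drop-out through withdrawal and death, not with administrative truncation on 31/10/18.

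**Conclusion.** The point holds, mainly for hospital stays. The main analysis reduces a stated count to any/none, pools risks that differ about twofold by length of follow-up, and gives up about 22% to 31% of the information under Poisson, or about 41% with dispersion 1. These figures rest on a constant rate of 0.70 per resident-year from one external needs assessment. The power comparison also assumes that half the residents are truncated and a rate ratio of 0.7.

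For death the point is smaller. The odds ratio has no defined time horizon under calendar truncation, and a Cox model repairs that and handles administrative censoring. It brings almost no gain in power. Bias between arms in either outcome would need withdrawal to differ by arm and also to be left unhandled by the methods in section 18.1; the documents establish neither.

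**What to change.** In the section 18.2 table:

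- **Hospital stays:** make the Poisson or negative binomial regression of the number of stays, with log observed time as offset, the main analysis. Move logistic regression to sensitivity.
- **Death:** make the Cox model from randomisation, censored at last observation or 31/10/18, the main analysis. Move logistic regression to sensitivity and state its time horizon.

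No new data are needed, because the weekly records already cover the follow-up period. There are statistical costs. The offset treats time cut short by death or withdrawal as non-informative. The Cox model assumes proportional hazards and non-informative censoring, which section 18.1 itself questions for health-related moves, so the planned sensitivity analyses should be applied to these models too.

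There is also a procedural cost. Protocol version 4.0 is dated 15/04/2019, after record collection was due to end. The swap should be justified, dated and documented before unblinding.

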## 5 Trial objectives and outcomes

**HYPOTHESIS (Primary):** Daily oral probiotic reduces CAAD for infection vs placebo in CHR.

**HYPOTHESIS (Mechanisms):** Daily oral probiotic reduces gastrointestinal colonisation with AMR bacteria, enhances influenza vaccine response and modulates *ex-vivo* cytokine and chemokine response to Toll Like Receptor (TLR) agonists vs placebo in CHR.

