### **Secondary Mechanistic Outcomes**

Previous research has found a 40% prevalence of multi-drug resistant *E. coli* in faecal samples of UK nursing home residents (3) and a 37% prevalence of oral candida in hospitalised elderly patients (48). A meta-analysis of 6 trials of probiotics in critically ill patients reported probiotics reduced colonisation with multi-drug resistant gram negatives (OR 0.39 (95% CI: 0.16 to 0.95) (13). Despite high prevalence of AMR colonisation in CHR few studies have measured the effect of probiotics on this outcome. Hatakka et al (2006) found probiotics reduced the risk of oral candida in 276 older people by 75% (OR = 0.25, 95%CI 0.10- 0.65) (49). Stool and saliva samples at 6 to 12 months will provide 90% power at the 5% level to detect a 19% absolute reduction antimicrobial resistant bacteria and oral candida, assuming a 30% drop-out rate.

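### The Gram-negative row of the antimicrobial resistance analyses (protocol 18.2) omits the resistance criterion that the hypothesis, outcome measure and power statement require

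*Protocol*

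**What the plan says.** The mechanisms hypothesis in section 5 is "Daily oral probiotic reduces gastrointestinal colonisation with AMR bacteria". In the table in 5.1 the objective is "Gastrointestinal colonisation with antimicrobial resistant (AMR) bacteria", and the measure is "Culture and antibiotic sensitivity of Gram-negative Enterobacteriaceae and vancomycin resistant enterococci (VRE) from stool sample". Section 17.2, under Secondary Mechanistic Outcomes, starts from a "40% prevalence of multi-drug resistant" *E. coli* in nursing home residents and cites an odds ratio of 0.39 for multi-drug resistant Gram-negatives. It then claims 90% power at the 5% level for a 19-point absolute reduction in resistant bacteria and oral candida, allowing for 30% drop-out.

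The analysis table in 18.2 has two rows in its antimicrobial resistance block. One is "Vancomycin resistant enterococci in stools". The other is "Presence of Gram-negative isolates in stools". Both are analysed by separate logistic regressions at 3 and 12 months, each controlling for the baseline stool finding.

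**The concern.** The VRE row names resistance. The Gram-negative row does not, nor does it limit the organisms to Enterobacteriaceae. As worded, it makes the binary outcome the presence or absence of any Gram-negative isolate.

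That is a different endpoint from the one in section 5. A resident whose resistant *E. coli* is replaced by sensitive *E. coli* has the benefit that the hypothesis describes, yet is scored as present both before and after. The analysis could report little or no effect although resistance had fallen. The power figure in 17.2 would also be attached to an outcome for which it was not calculated.

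**Working it through.** **1. Which endpoint was powered?** Inputs from 17.1 and 17.2: 1:1 allocation, 5% level (two-sided assumed, since the protocol does not say), 19-point reduction, 30% drop-out, original target of 330. Evaluable per arm: n = 330 × 0.7 / 2 = 115.5.

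Power = Φ{[d√n − 1.96√(2p̄(1−p̄))] / √(p₁(1−p₁) + p₂(1−p₂))}, where d = p₁ − p₂ and p̄ is the mean of p₁ and p₂.

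- Resistant Gram-negatives, 40% vs 21%: [0.19 × 10.747 − 1.96 × 0.651] / 0.637 = 1.20, so power is 88.5%.
- Oral candida, from the "37% prevalence of oral candida in hospitalised elderly patients", 37% vs 18%: power is 90.4%.

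Both are close to the stated 90%. The change from 40% to 21% is an odds ratio of (0.21/0.79)/(0.40/0.60) = 0.40, next to the cited 0.39. The power statement is therefore about resistant carriage.

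**2. The row read as resistant carriage.** The statement carries over: 88.5% at 330. At the current target of 258 to 270 the same inputs give 79.7% to 81.5%. That shortfall is a separate matter from the wording of the row.

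**3. The row read literally.** Let f be the share of residents losing resistant strains who also lose every Gram-negative isolate. A 19-point fall in resistant carriage then appears as 19 × f points. The protocol gives neither f nor the overall prevalence, so both are assumed here. The range below is for overall carriage of 70% to 98%, with 30% drop-out.

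| f | Visible difference | Power, 330 randomised | Power, 258 randomised |
|---|---|---|---|
| 1 | 19 points | 84.4% to 99.6% | 74.7% to 98.4% |
| 0.5 | 9.5 points | 32.8% to 82.5% | 26.7% to 72.4% |
| 0.25 | 4.75 points | 11.7% to 42.2% | 10.0% to 34.4% |
| 0 | 0 points | nothing to detect | nothing to detect |

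**4. Are the sensitivity results analysed between arms elsewhere?** No other row in 18.2 uses the Gram-negative sensitivity results. The tertiary objective in 5.1 relates baseline vitamin D to colonisation with resistant bacteria. The mediation analysis in 18.1 runs through antimicrobial resistance, which it does not define. Both need a resistance variable, but neither is a comparison of resistant Gram-negative carriage between arms.

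**The case against.** The best defence is that the row is shorthand. It stands in a block headed antimicrobial resistance, section 9 sends the reader to section 5 for outcome definitions, and section 5 specifies sensitivity testing. The synopsis also describes the stool measure in terms of resistant bacteria. On this view only an adjective is missing, and the drugs and breakpoints belong in the SAP.

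Much of this stands. Resistance was probably intended, and the detailed definition can properly be left to the SAP. But a block heading does not change the binary outcome that the row states, and the neighbouring row shows that the table names resistance when it means it. An SAP that followed the row would miss the objective; one that followed section 5 would depart from the row.

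Three stronger readings are tempting and are not supported:

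- A reader might infer that the resistance hypothesis goes untested. The VRE row tests part of it, although VRE is not the organism behind the 40%.
- A reader might infer that the sensitivity data are never used. The tertiary and mediation analyses plan to use resistance data.
- A reader might infer that the endpoint has to be multi-drug resistance. That term appears in 17.2 only in the background figures; section 5 and the power sentence itself speak of antimicrobial resistance more broadly, so requiring it would narrow the stated objective.

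**Conclusion.** The inconsistency is real and should be corrected, though it concerns one row for a secondary outcome. The Gram-negative analysis as worded does not measure what section 5 sets out and 17.2 powers.

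Its size cannot be given as one number. Complete replacement by sensitive strains would make the effect invisible; if everyone who lost resistant strains lost all Gram-negatives, nothing would be hidden. The intermediate figures rest on assumed prevalences and an assumed share f. A reader might also infer that near-universal carriage by itself would ruin the analysis. The table does not show this: for a fixed absolute difference, power rises with prevalence. What matters is how much of the fall in resistance is also a loss of all Gram-negatives. What is certain is that the protocol supplies no basis for applying its 90% to the row as written.

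**What to change.** Reword the row in 18.2 to *Presence of antimicrobial-resistant Gram-negative Enterobacteriaceae in stools*, derived from the sensitivity results and consistent with section 5. Fix the definition of resistance before unblinding, in the SAP if preferred. Code a valid sample with no resistant isolate as 0, and leave a missing sample as missing. The planned logistic regressions can stay as they are.

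If the power in 17.2 is to be cited for this outcome, add a multi-drug resistant version that matches the 40% assumption. Keep presence of any Gram-negative isolate as a descriptive summary.

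The cost is a change of table wording and one derived variable (two with the multi-drug resistant version). The sensitivity testing is already planned, so no new samples or assays are needed.

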## **18 Analysis**

### **18.1 Main analysis**

The primary analysis will be by intention-to-treat, and will consist of a between-group comparison of the mean cumulative antibiotic administration days (CAAD) using Poisson regression. As the randomisation will be stratified by care home, the regression model will control for the care home a participant was recruited from. Negative binomial regression will be used in the presence of over-dispersed count data.

For secondary outcomes, depending on the type of data, a mixture of Poisson, linear, logistic and Cox models will be used to appropriately compare trial arms with respect to rates, means, proportions and time to events (see table below for more details).

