Clostridium difficile in stools	Two logistic regressions (stool sample finding at 3/12 months separately) controlling for baseline stool sample finding.	
Presence of oral candidiasis	Two logistic regressions (response at 3/12 months separately) controlling for baseline response.	
Amount of oral candidiasis present in saliva	Two ordinal regressions (response at 3/12 months separately) controlling for baseline response.	
L. rhamnosus GG in stools	Two linear regressions (stool sample finding at 3/12 months separately) controlling for baseline stool sample finding.	Transformations for normality.
Bifidobacterium animalis subsp. lactis (BB-12)	Two linear regressions (stool sample finding at 3/12 months separately) controlling for baseline stool sample finding.	Transformations for normality.
Full blood count	Linear regression	Transformations for normality.
Flu vaccine response - titer	Linear regression	Transformations for normality.
Flu vaccine response - seroconversion and seroprotection	Logistic regression	

\* All sensitivity analyses will include a consideration of adherence to study product and the impact of missing data / deaths.

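### The section 18.2 table names no baseline covariate for the immune parameters or full blood count, although baseline values are collected and other repeated measures are baseline-adjusted

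*Protocol*

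**What the plan says.** Section 18.1 of the Protocol refers the reader to the section 18.2 table for the secondary analyses ("see table below for more details").

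In that table, three rows name linear regression alone, with transformation for normality as the only sensitivity entry besides the general footnote on adherence, missing data and deaths:

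- "Immune parameters -Immune cell phenotypes -TLR ligand stimulated cytokines/chemokines -Plasma cytokines/chemokines -Monocyte and neutrophil phagocytosis -Flu vaccine response"
- "Full blood count"
- "Flu vaccine response - titer"

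Nine rows for other measures repeated from baseline do name the baseline covariate: EQ5D, ICECAP-O, Gram-negative isolates, VRE, *C. difficile*, presence and amount of oral Candida, LGG and BB-12. The EQ5D row, for example, reads "Two linear regressions (EQ5D at 3/12 months separately) controlling for baseline EQ5D". The LGG and BB-12 rows, in the same mechanistic block as the immune parameters, read "Two linear regressions (stool sample finding at 3/12 months separately) controlling for baseline stool sample finding".

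On timing, section 5.1 schedules the cytokine, chemokine and phagocytosis measurements at "Baseline and up to 12* months". It places immune phenotyping with the full blood count, which is taken from everyone at baseline and repeated in a subset. Sections 15.3 and 25 agree that these samples exist at both ends. The influenza samples follow a different clock: "Sample taken on the day of (or up to 10 days prior to), and 4 weeks (28 days) post influenza vaccination", in participants who have already taken study product for at least two months.

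**The concern.** The table fixes covariates row by row and does so unevenly. A reader who finds baseline adjustment written out nine times, including in the same mechanistic block, cannot tell whether its absence from the immune and blood count rows is deliberate.

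Modulated ex-vivo cytokine and chemokine response is part of the mechanisms hypothesis in section 5, and the immunology sample is only about 100 people. The power statement for mechanistic outcomes in section 17.2 covers antimicrobial-resistant bacteria and oral Candida only, so nothing in the Protocol shows that the immune comparison has precision to spare. Leaving out the baseline value keeps stable differences between people in the error term. It also leaves the covariate choice open across many cytokine, chemokine and cell-phenotype endpoints.

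**Working it through.** The Protocol gives no power, SD, effect size or baseline-to-follow-up correlation for these outcomes, so there is no stated figure to reproduce. The check asks how much precision the baseline term would buy.

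**Inputs from the Protocol.** Allocation is 1:1 (section 17.1). The immunology sample is about 100 (sections 5.1 and 15.3). The follow-up blood count is about 150 in section 15.3 but about 100 in section 5.1. The influenza sub-study has no stated size.

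**Assumptions.** Correlation *r* between baseline and follow-up of 0.3, 0.5 or 0.7; a true difference of 0.5 SD; two-sided 5% level; 50 complete pairs per arm.

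**Formulae.** With SD = 1, the variance of the unadjusted difference is 2/50 = 4/100 = 0.04, so its standard error is 0.20. Adjusting for baseline multiplies the variance by 1 − r². Then:

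- power = Φ(0.5 / √[(1 − r²) × 0.04] − 1.96)
- smallest difference detectable with 80% power = (1.96 + 0.842) × 0.20 × √(1 − r²)
- equivalent unadjusted sample = 100 / (1 − r²)

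| r | Variance ratio | Power for 0.5 SD | Detectable difference | Equivalent N |
|---|---|---|---|---|
| no baseline term | 1.00 | Φ(2.50 − 1.96) = 70.5% | 0.56 SD | 100 |
| 0.3 | 0.91 | Φ(2.62 − 1.96) = 74.6% | 0.54 SD | 110 |
| 0.5 | 0.75 | Φ(2.89 − 1.96) = 82.3% | 0.49 SD | 133 |
| 0.7 | 0.51 | Φ(3.50 − 1.96) = 93.8% | 0.40 SD | 196 |

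A simulation with 50 per arm and 4,000 runs agreed: power was 69% without the baseline term, and 73%, 82% and 94% with it.

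**Other sample sizes.** If 30% of the 100 are lost (the drop-out rate that section 17.2 uses for other outcomes), 70 remain. Power for 0.5 SD is then 55.2% without the term and 59.2%, 67.6% or 83.4% with it. With 150 complete blood counts it is 86.5% without the term and 89.4%, 94.2% or 99.0% with it.

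**Influenza titre.** These figures do not carry over. Participants must have taken study product for at least two months before vaccination, so the pre-vaccination titre is a post-randomisation value. The schedule in section 25 draws no influenza sample at randomisation. If the product changes the pre-vaccination titre, adjusting for it conditions on something that treatment has affected.

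**The case against.** The strongest reply is that the Protocol nowhere says these comparisons are unadjusted. A reader might infer that from the bare model name, but the table is shorthand. The primary outcome row names only Poisson regression, while section 18.1 says that model controls for care home. An unseen statistical analysis plan may already include the baseline value. This stands, so the point is that no baseline covariate is specified, not that a wrong analysis is prescribed. It does not remove the point, because the same table does specify that covariate for the other repeated measures.

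A reader might also infer that the results would be biased. The documents do not support that. Under randomisation with complete follow-up, the comparison without the baseline term is unbiased, and its standard error already allows for chance imbalance at baseline.

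Third, it is tempting to describe all three rows as a sub-study of about 100 and to treat the pre-vaccination titre as a missing baseline. The figure of about 100 is secure only for immunology, and the titre is not a baseline. Leaving it out of the main comparison is defensible. The Protocol also does not say whether the titre outcome is the post-vaccination value or the rise.

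Finally, the size of the gain rests on assumed values. At *r* = 0.3 it is only four percentage points. The gain at *r* = 0.7 requires that correlation between samples taken up to 12 months apart.

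**Conclusion.** The point holds for the full blood count and for the immune parameters other than influenza response. Baseline values are collected, the table adjusts for baseline in its other repeated measures, and these two rows do not say so. The consequence is lost precision, not invalidity, and the primary outcome is untouched.

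The direction is the same for any non-zero correlation large enough to repay the one degree of freedom spent. The size cannot be fixed from the documents: the variance reduction is 9%, 25% or 49% for assumed correlations of 0.3, 0.5 or 0.7. The corresponding rise in power, from about 71% to 75%, 82% or 94%, also assumes 100 complete pairs and a 0.5 SD difference. The point does not extend to the influenza titre, where adjustment answers a different, conditional question. It is best classed as a free improvement.

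**What to change.** 1. In the section 18.2 table, add control for the baseline value to the full blood count row and to the immune-parameter row, excluding that row's influenza entry. Where the outcome is transformed, use the baseline value on the same scale.
2. Take influenza response out of the immune-parameter row, so that one rule does not cover measures with and without a randomisation baseline.
3. For influenza titre, keep the comparison without the pre-vaccination titre as the main analysis. Show the model adjusted for log pre-vaccination titre as supplementary, labelled as conditional on a value that treatment may have affected.

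The cost is table wording. No new samples or visits are needed.
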